## 11 Trial assessments and procedures

#### 11.1 Overview

Assessments and procedures to be conducted at each visit are listed in the schedule of trial procedures (Section 4) and will be conducted in the order presented in Panel 6.

Panel 6: Sequence of assessments

**Abbreviations:** IMP = investigational medicinal product.

- Laboratory assessments include PK and PD samples. PD samples include serum biomarkers, skin biopsies and tape strips.
- b. For the first 3 treatment visits (i.e., Visits 3, 4, and 5) subjects will be monitored after injections for immediate drug reactions for a minimum of 1 hour with vital signs taken immediately after injections as well as after 30 minutes (± 5 minutes) and after 1 hour (± 5 minutes), or until stable, whichever is later.

Subjects participating in the trial will be under careful supervision of a qualified principal investigator who must be a dermatologist or an allergist. Investigators must be physicians and have experience in treating AD as well as documented experience with and/or training in the assessments used in this trial. All dermatologic assessments must be performed by a dermatologist or an adequately qualified medical doctor (defined as someone with at least 1 year post graduate experience).

AEs must be assessed by a physician (see details in Section 13.2).

To reduce inter-rater variability, the same investigator should, whenever possible, perform all the efficacy assessments for a given subject throughout the entire trial period.

Version: 5.0

The investigators performing the assessments must not be involved in the preparation and administration of IMP (Section 9.3.2).

### 11.2 Assessments performed only at screening/baseline

### 11.2.1 Demographics

The following demographic data will be recorded:

- Age.
- Sex: female, male.
- Race: American Indian or Alaska native, Asian, Black or African American, native Hawaiian or other Pacific islander, White, other (if other, a specification should be provided).
- Ethnic origin (self-reported by the subject): "Hispanic" or "Latino", not "Hispanic or Latino".

#### 11.2.2 Medical history

Relevant medical history must be recorded:

- Skin disease history and atopy history including:
  - Age at first onset of AD.
  - Asthma.
  - Food allergy.
  - Hay fever.

For each condition or diagnosis, the start date and stop date will be recorded (it will also be recorded if the diagnosis is ongoing).

• Other medical and surgical history including concurrent diagnoses within the previous 12 months. For each condition, diagnosis, or surgical procedure, the start date and stop date will be recorded (it will also be recorded if the condition, diagnosis, or surgical procedure is ongoing).

Relevant medical history also includes diseases which are specifically listed as exclusion criteria and diseases for which specific treatments are listed as exclusion criteria.

### 11.2.3 **Height**

The subject's height (without shoes) will be measured according to the schedule of trial procedure (Section 4).

### 11.3 Efficacy assessments

### 11.3.1 Validated Investigator Global Assessment Scale for Atopic Dermatitis

The validated Investigator Global Assessment Scale for Atopic Dermatitis (vIGA-AD) is an instrument used in clinical trials to assess the subject's global disease severity and is based on a 5-point scale ranging from 0 (clear) to 4 (severe) (Panel 7) [47]. The vIGA-AD score will be assessed according to the schedule of trial procedures (Section 4). The assessment will be based on the condition of the disease at the time of evaluation and not in relation to the condition at a previous visit. The disease severity assessment score will be recorded in the eCRF.

Panel 7: Validated Investigator Global Assessment Scale for Atopic Dermatitis

Score	Morphological description
0 – Clear	No inflammatory signs of atopic dermatitis (no erythema, no induration/papulation, no lichenification, no oozing/crusting). Post-inflammatory hyperpigmentation and/or hypopigmentation may be present.
1 - Almost clear	Barely perceptible erythema, and barely perceptible induration/papulation, and/or minimal lichenification. No oozing or crusting.
2 – Mild	Slight but definite erythema (pink), slight but definite induration/papulation, and/or slight but definite lichenification. No oozing or crusting.
3 - Moderate	Clearly perceptible erythema (dull red), clearly perceptible induration/papulation, and/or clearly perceptible lichenification. Oozing and crusting may be present.
4 – Severe	Marked erythema (deep or bright red), marked induration/papulation, and/or marked lichenification. Disease is widespread in extent. Oozing or crusting may be present.

#### 11.3.2 Body surface area involvement

The total BSA score will be assessed according to the schedule of procedures (Section 4).

The investigator will assess the total AD involvement for the whole body, i.e. head/neck, upper extremities, trunk, genitalia, and lower extremities, as a percentage of the total BSA. As a guidance for this estimate, the surface of a full, flat palm (including the 5 fingers) of an adult subject corresponds to approximately 1% of the total BSA.

#### 11.3.3 Eczema Area and Severity Index

The Eczema Area and Severity Index (EASI) is a validated measure used in clinical practice and clinical trials to assess the severity and extent of AD [48]. The EASI score will be assessed according to the schedule of trial procedures (Section 4). The assessment will be based on the condition of the disease at the time of evaluation and not in relation to the condition at a previous visit.

Trial ID: LP0145-2274 Date: **04-Jan-2023** Version: 5.0 Page 72 of 129

The EASI is a composite index with scores ranging from 0 to 72, with higher values indicating more severe or more extensive condition. The index will be calculated as shown in Panel 8. Briefly, the investigator will assess the severity of 4 AD disease characteristics (erythema, induration/papulation, excoriation, and lichenification) on the 4 body regions (head/neck, trunk, upper extremities, lower extremities); severity will be assessed according to the scale shown in Panel 9. For each body region, a severity sum score will be calculated which will be multiplied by an area score (Panel 9) and by a weighting factor. The EASI score equals the sum of the scores obtained for each body region (Panel 8).

The body region, severity of the disease characteristics (erythema, induration/papulation, excoriation, and lichenification), and the area score will be recorded in the eCRF.

Panel 8: Calculation of the EASI score

Body region	Erythema	Induration/ papulation	Excoriation	Lichenification	Area score	Weighting factor	Score
Head/neck	(SS +	SS +	SS +	SS)	× AS	× 0.1	
Trunk	(SS +	SS +	SS +	SS)	× AS	× 0.3	
Upper extremities	(SS +	SS +	SS +	SS)	× AS	× 0.2	
Lower extremities	(SS +	SS +	SS +	SS)	× AS	× 0.4	
		The EASI	score is the s	sum of the	4 body reg	on scores	(range 0-72)

**Abbreviations:** AS = area score; EASI = Eczema Area and Severity Index; SS = severity score. Modified from [49].

Page 73 of 129

Panel 9: EASI severity score scale and area score scale

Severity score scale				
0	None/absent			
1	Mild			
2	Moderate			
3	Severe			

Note: half-steps (0.5, 1.5, 2.5) are allowed.

Area score scale				
0	0% affected area			
1	1% to 9% affected area			
2	10% to 29% affected area			
3	30% to 49% affected area			
4	50% to 69% affected area			
5	70% to 89% affected area			
6	90% to 100% affected area			

**Abbreviations:** EASI = Eczema Area and Severity Index.

# 11.4 Safety assessments

#### 11.4.1 Vital signs

Vital signs (blood pressure, pulse, and body temperature) will be assessed according to the schedule of trial procedures (Section 4). At an unscheduled visit, it will be at the discretion of the investigator if vital signs should be assessed.

For the first 3 IMP treatment visits (i.e. visits 3, 4, and 5) subjects will be monitored after IMP administration for immediate drug reactions for a minimum of 1 hour with vital signs taken immediately after IMP administration as well as after 30 minutes ( $\pm$  5 minutes) and after 1 hour ( $\pm$  5 minutes), or until stable, whichever is later.

Vital signs (blood pressure, pulse, and body temperature) will be assessed following at least 5 minutes of rest. If a subject presents with an abnormal vital sign, the measurement of the vital sign can be repeated approximately 2–5 minutes later to verify the first measurement. Should the repeated measurement result in a normal value, the measurement must be repeated once more. If the third measurement verifies the second (normal) value, the first measurement should be considered false and the third measurement should be recorded in the eCRF. If the third measurement confirms the first measurement (abnormal), the second measurement should be considered false and the third measurement should be recorded in the eCRF. Only the last measurement considered true should be recorded in the eCRF.

In case of a clinically significant abnormal vital sign at screening and/or baseline, it will be at the discretion of the investigator if the subject should be included in the trial in accordance

with exclusion criterion 31. During the trial, if a subject presents with a clinically significant abnormal vital sign, the investigator must take appropriate action, at their discretion.

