## 14.3.9.2 Vital signs and physical examination

The change in vital signs (blood pressure, pulse, and body temperature) from baseline to each relevant visit will be summarized by treatment group as mean, standard deviation (SD), median, minimum and maximum values for the safety analysis set.

Subjects with abnormal, clinically significant physical findings will be listed. Furthermore, a shift table for physical findings showing the change from baseline to week 16 in clinical assessments (normal; abnormal, not clinically significant; abnormal, clinically significant) will be performed.

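### The vital-sign repeat rule keeps a repeated first reading out of the eCRF, so a real but very short change after injection at visits 3 to 5 can be lost

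*Combined protocol and SAP*

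**What the plan says.** The repeat rule is in protocol Section 11.4.1. After an abnormal reading, "the measurement of the vital sign can be repeated approximately 2–5 minutes later to verify the first measurement". The repeat is optional, and no section asks for a normal first reading to be checked again. From there the steps are fixed:

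- Second reading normal: "Should the repeated measurement result in a normal value, the measurement must be repeated once more".
- Third reading also normal: "If the third measurement verifies the second (normal) value, the first measurement should be considered false", and the third value is entered.
- Third reading abnormal: "If the third measurement confirms the first measurement (abnormal), the second measurement should be considered false", and the abnormal third value is entered.
- In every case: "Only the last measurement considered true should be recorded in the eCRF".

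The same section sets the post-dose monitoring. For visits 3 to 5 the requirement is that "subjects will be monitored after IMP administration for immediate drug reactions for a minimum of 1 hour with vital signs taken immediately after IMP administration"; further readings follow at 30 minutes and 1 hour, or until stable if that is later. Section 9.2 (After IMP administration) says that these readings go into the eCRF. The repeat rule makes no exception for them. The paragraph containing it also asks for at least 5 minutes of rest before any vital sign is taken.

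For the analysis, Section 14.3.9.2 says: "The change in vital signs (blood pressure, pulse, and body temperature) from baseline to each relevant visit will be summarized by treatment group", using mean, SD, median, minimum and maximum. It does not say whether the post-injection time points are among the values summarised. The listing and shift table in that section concern physical findings, not vital signs.

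**The concern.** Re-measurement works in one direction. A falsely abnormal first reading can be corrected, but a falsely normal one cannot. Once any repeat is taken, the first value is not the one recorded.

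For a resting reading at a routine visit, that is ordinary verification with a modest side effect. For a reading taken straight after injection it is different, because a brief abnormal value that soon returns to normal is one of the things the monitoring is there to find. Two normal repeats do not show that such a reading was an error; they are also what a short real reaction would produce. The rule treats the two alike and keeps neither in the database.

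At stake are the vital-sign safety tables and any later look at immediate reactions. The primary endpoint is not touched.

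**Working it through.** The plan gives no figure for this rule, so there is none to reproduce. The check codes the rule as written and applies it to assumed blood-pressure values.

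**Coding.** Normal first reading: record it. Abnormal then abnormal: record the second (the text covers this branch only through the sentence on the last true measurement). Abnormal then normal: record the third. Each scenario used 2,000,000 simulated draws.

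**From the protocol.** First repeat at 2 to 5 minutes. The interval to the third reading is not stated; taking it as equal, the sequence ends after 2 × 2 = 4 to 2 × 5 = 10 minutes. Sample size is 8 + 4 evaluable subjects (Section 14.1).

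**Assumed, not in the documents.** Systolic limits 90 to 140 mmHg; every abnormal value repeated unless stated otherwise.

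**Step 1: one deterministic case.** A subject at 120 mmHg has a 40 mmHg rise with a 2-minute half-life, and readings are 5 minutes apart. The rise at time t is 40 × 2^(−t/2).

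- t = 0: 40, reading 160, abnormal.
- t = 5: 40 × 2^(−2.5) = 7.07, reading 127.1, normal.
- t = 10: 40 × 2^(−5) = 1.25, reading 121.25, normal.

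The recorded change is 1.25 instead of 40 mmHg. With a 30-minute half-life, the second reading is 120 + 40 × 2^(−5/30) = 120 + 35.64 = 155.6, still abnormal, so the recorded change is 35.6. To be lost, a change must be back within limits at the second reading and still so at the third.

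**Step 2: the same with variation.** Between-subject SD 10 and within-subject SD 5 around 120 mmHg; rise of 25 or 40 mmHg; spacing 2 or 5 minutes.

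| Half-life of the rise | Abnormal immediate readings still recorded as abnormal |
|---|---|
| 2 min | 14% (5-min spacing); 39% to 53% (2-min spacing) |
| 5 min | 39% to 87% |
| 15 min | 74% to 97% |
| 30 min | 85% to 99% |
| 60 min | 90% to 99% |

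For the 40 mmHg rise, 2-minute half-life and 5-minute spacing, the mean recorded change is 3.7 instead of 40 mmHg. The scheduled 30-minute reading does not recover short changes: with half-lives of 2 to 5 minutes it is abnormal in only about 4% to 6% of those whose first reading was abnormal.

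**Step 3: what one lost reading does to a table.** Suppose one of 8 subjects has the Step 1 change and the other seven have none. With the first reading the summary is mean 40/8 = 5.0, maximum 40, SD √[(1600 − 8 × 25)/7] = 14.1. With the recorded value it is mean 1.25/8 = 0.16, maximum 1.25, SD 0.44.

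**Step 4: routine resting readings.** True mean 120 to 130 mmHg, between-subject SD 10 to 12, within-subject SD 4 to 8.

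- All abnormal values repeated: the mean is 0.06 to 0.94 mmHg lower and the SD about 1% to 6% smaller.
- Half repeated: the mean is 0.03 to 0.47 mmHg lower.
- Limits symmetric about the mean, 10% or 20% of first readings abnormal: the mean shift is 0.00 SD; the spread shrinks about 2% to 3% at a within-visit correlation of 0.9 and 6% to 8% at 0.7.
- Share abnormal at mean 120, SDs 10 and 8: first reading 6.9%, recorded 3.3%, truly abnormal (by the subject's own level) 2.4%. Here the rule mainly removes false positives.

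**The case against.** The other side has a good deal on its side. Repeating is optional. A persistent abnormality, or one confirmed at the third reading, is recorded. The rule applies equally at baseline and in both arms under blinded assessment, so much of the noise effect can cancel in change from baseline and between arms. New clinically significant signs remain reportable as adverse events (Section 11.4.1, Reporting in eCRF), and monitoring continues until the subject is stable. The tables are descriptive, with no tests. The 5-minute rest sentence even leaves it unclear whether the repeat rule was meant for the immediate post-injection reading.

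Most of this stands, and it rules out three stronger readings.

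- A reader might infer that recorded vital signs in general are materially biased towards normal. Step 4 does not support that.
- A reader might treat repeats as independent, so that an abnormal probability p is recorded as p²(2 − p) and 10% becomes 1.9%. Readings minutes apart in one person are not independent, the plan does not tabulate proportions of abnormal vital signs, and part of any fall is correct removal of false positives.
- A reader might say that the first values are erased for good. The rule governs only what enters the eCRF; no section orders deletion from source, and Appendix 3D requires source documents to be archived.

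What does not stand is that the other safeguards close the gap. Equal application does not cancel a real post-injection effect in one arm. Adverse-event reporting covers clinically significant signs, and a reading that the protocol has declared false may well not reach that route. The ambiguity over the rest period is itself something to settle.

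**Conclusion.** The point holds in a narrow form. As written, the rule can label a real post-injection change at visits 3 to 5 as false and keep it out of the eCRF when the change has gone by the two repeats, about 4 to 10 minutes. It would then be missing from the change summaries wherever those time points are summarised, with most effect on minimum, maximum and SD in groups of 8 and 4. Longer changes are mostly kept. For routine resting readings the effect is under about 1 mmHg in the mean and partly beneficial.

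The sizes rest on assumed limits, variances, repeat rates and equal spacing of repeats, none of which the protocol gives. The direction for short post-injection changes follows from the wording alone. This is a cheap improvement to data capture and does not threaten the trial's conclusions.

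**What to change.** In Section 11.4.1, enter every reading with its time in the eCRF, and state that repeats do not replace the scheduled post-injection readings at visits 3 to 5. Investigators can still repeat a reading to verify it, so clinical handling is unchanged. Section 11.4.4 already works this way for ECGs, where the individual measurements are kept alongside their average.

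In Section 14.3.9.2, list all vital-sign readings and say whether the post-injection time points are summarised; if so, summarise them from the first reading. For routine visits, keep the verified reading as the main summary and add a first-reading sensitivity summary. Using first readings alone there would let cuff and technique artefacts set the extremes in such small groups.

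Reconcile the 5-minute rest requirement with the reading due immediately after administration, since both cannot apply literally to the same measurement.

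The cost is a few more eCRF fields per repeat (the repeated value or values and the time), one more listing and one more summary table, and slightly noisier extremes.

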# Reporting in eCRF

It will be recorded in the eCRF if vital signs were measured; if not, a reason should be provided. Vital signs, arm used to measure blood pressure, the temperature measuring method (axillary, ear, oral, rectal, other), and the date and time vital signs were measured will be recorded in the eCRF. Clinically significant abnormal vital signs at the screening visit and baseline (as the subjects has not been administered treatment) will be documented as medical history in the eCRF. At subsequent visits, any clinically significant deterioration of a pre-existing condition as well as any new clinically significant sign, symptom, or illness occurring after randomisation will be reported as an AE in accordance with Section 13.3.

## 11.4.2 Physical examination

A physical examination of the subject including general appearance, regional lymph nodes, and dermatologic examination of the skin will be performed according to the schedule of trial procedures (Section 4). At an unscheduled visit, it will be at the discretion of the investigator if a physical examination should be performed.

In case of a clinically significant abnormal finding during physical examination at screening and/or baseline, it will be at the discretion of the investigator if the subject should be included in the trial in accordance with exclusion criterion no. 31. During the trial, if a subject presents with a clinically significant abnormal finding during physical examination, the investigator must take appropriate action, at their discretion.

#### Reporting in eCRF

It will be recorded in the eCRF if a physical examination was conducted. If not, a reason should be provided. The investigator's evaluation of the physical examination ('normal', 'abnormal, not clinically significant', 'abnormal, clinically significant') will also be recorded.

Clinically significant abnormal findings during physical examination at screening and baseline will be documented as medical history in the eCRF. At subsequent visits, any new clinically significant abnormal findings, symptoms, or illnesses, as well as any clinically significant deterioration of a pre-existing condition after randomisation will be reported as an AE in accordance with Section 13.3.

## 11.4.3 Weight

Weight will be recorded according to the schedule of trial procedures (Section 4). The subject's weight (in indoor clothing and without shoes) will be measured. At an unscheduled visit, it will be at the discretion of the investigator if weight should be measured.

## 11.4.4 Electrocardiography

ECGs must be measured according to the schedule of trial procedures in (Section 4). At an unscheduled visit, it will be at the discretion of the investigator if an ECG should be measured.

At the respective visit, the individual measurements as well as the average of 3 consecutive 12-lead resting digital ECG will be recorded after the subject has been in supine position for at least 5 minutes. ECGs must be measured before any blood samples scheduled at the same visit.

A pre-evaluation of the ECGs will be performed by the investigator to evaluate immediate subject safety. At a minimum, the date of ECG pre-evaluation will be recorded in the source documents. In case of a suspected abnormal ECG, the investigator must take appropriate action, at their discretion.

The ECG data will be transferred to a central ECG service company for central evaluation. A cardiologist at the ECG service company will analyse and interpret the ECG data. The ECG service company will provide ECG evaluation reports to the trial sites.

The investigator must evaluate all abnormal ECG results ('clinically significant' or 'not clinically significant') and sign and date. The investigator is responsible for taking the final decision about the clinical significance of any abnormal ECG.

If a result is abnormal at the screening or baseline visit and considered by the investigator to be clinically significant, it will be up to the investigator's discretion to decide if the subject should be enrolled into the trial (respecting exclusion criteria no. 21 and 31). If a subject with an abnormal and clinically significant ECG result is enrolled, the investigator should provide a justification in the medical record.

During the trial, if a subject presents with a clinically significant abnormal ECG or a clinically significant abnormal change in ECG from baseline, the ECG should be repeated. If the ECG or change in ECG is confirmed clinically significantly abnormal, the subject must permanently discontinue IMP, and be withdrawn from the trial.

Trial ID: LP0145-2274 Date: **04-Jan-2023** Version: 5.0 Page 76 of 129

The collection and transmission of ECG data will be described in a separate ECG manual.

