#### Safety follow-up period (week 17 to week 32)

In the safety follow-up period, the subject will not receive any treatment with LEO 138559 or comparator injections. The safety of the subject will further be assessed at 3 safety follow-up phone calls (weeks 20, 24, and 28) and at a final safety follow-up visit at week 32. Topical treatment for AD will be permissible during the safety follow-up period. At the end of trial visit the diary will be collected and assessments will be conducted as specified in Panel 2.

Subjects who require treatment with other biologics will prematurely discontinue the trial.

Subjects who discontinue the trial early should be requested to return for an early termination / end of trial visit (see also Section 10.3) at the time of the decision to withdraw from the study.

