### 10 Discontinuation and withdrawal

## 10.1 General principles

A subject may withdraw from the trial (prior to first dose or during the treatment period) or permanently discontinue trial treatment at any time if the subject, the investigator, or LEO Pharma considers that it is not in the subject's best interest to continue.

A subject who withdraws from the trial is a subject who stops treatment with the IMP and all further protocol defined trial activities. A subject who permanently discontinues IMP is a subject who, although they stop treatment with the IMP, agree to their follow-up as described in Section 10.3. Early termination assessments to be conducted for both events are described in Section 10.3.

If a subject withdraws from the trial, they may request destruction of any samples taken and not tested. The investigator must document this in the subject's medical record and inform LEO Pharma.

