#### 10.2 Reasons for discontinuation of IMP

### 10.2.1 Reasons for permanent discontinuation of IMP

Subjects will permanently discontinue IMP in the event of:

- Withdrawal by subject
- An AE that, in the opinion of the investigator or sponsor's medical expert, contraindicates further dosing.
- Confirmed clinically significantly abnormal ECG or change in ECG.
- Initiation of prohibited medication which cannot be safely replaced by other non-prohibited medications.
- Evidence of pregnancy, or if the subject is noncompliant with the contraception requirements (see Section 8.2).
- Symptomatic infection with SARS-CoV-2 that is likely to have an impact on efficacy or safety data (i.e., patients with a SARS-CoV-2 infection without or very mild symptoms only (e.g., rhinitis or sore throat) might continue with the study at investigator's discretion and in accordance with the applicable local regulations)..
- Other reasons, at the discretion of the investigator. If other, a specification should be provided.

Page 66 of 129

It is not allowed to restart IMP treatment after discontinuation of IMP.

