### 10.3 Early termination assessments

#### Permanent discontinuation of IMP

Subjects who permanently discontinue IMP for any reason will be asked to attend an early termination visit as soon as possible after last administration of IMP and return to the trial site for additional visits as indicated below:

- An early IMP termination visit as soon as possible after last dose of IMP (in case of early termination before week 4: a nominal week 4 visit)
- An end of trial visit (safety follow-up visit 16 weeks after last administration of IMP).

See the schedule of trial procedures (Section 4) for data to be collected at these visits. The subjects will be asked to complete the diary until end of trial visit. The investigator will review any AEs which will be followed up according to Section 13.7, if the subject agrees.

Details on data to be recorded in the eCRF for subjects who permanently discontinue IMP can be found in Section 11.8.

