#### Withdrawal from trial

Subjects who withdraw from the trial after first dose of IMP for any reason will be asked to attend an early termination visit as soon as possible after last administration of IMP (see the schedule of trial procedures [Section 4] for data to be collected at an early termination visit). The investigator will review any AEs which will be followed up according to Section 13.7, if the subject agrees.

Details on data to be recorded in the eCRF for subjects who withdraw from the trial can be found in Section 11.8.

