#### **End-of-trial form**

An end-of-trial form must be completed in the eCRF for all screened subjects. The following data will be collected:

- Screening failure.
- Did the subject complete the trial?
- Which was the last visit (including phone calls) the subject attended in this trial?
- Date of last contact.
- Primary reason for withdrawing from the trial (death, pregnancy, adverse event, lack of efficacy, screening failure, withdrawal by subject, lost to follow-up, or other [if other, a specification should be provided]).
- If the subject attended the primary endpoint visit (visit 6). If not, the primary reason for not attending the visit (death, pregnancy, adverse event, lack of efficacy, withdrawal by subject, lost to follow-up, or other [if other, a specification should be provided]).
- If the subject attended the end-of-treatment visit (visit 12). If not, the primary reason for not attending the visit (death, pregnancy, adverse event, lack of efficacy, withdrawal by subject, lost to follow-up, or other [if other, a specification should be provided]).
- If the subject attended the safety follow-up visit (visit 16). If not, the primary reason for not attending the visit (death, pregnancy, adverse event, lack of efficacy, withdrawal by subject, lost to follow-up, or other [if other, a specification should be provided]).

The end of trial form will be completed when the subject turned out to be a screening failure or has had their last visit (that is the safety follow-up visit 16, or early IMP termination visit).

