## 14.3.6 Secondary endpoint analysis

The secondary endpoint

• Number of treatment-emergent adverse events from baseline to week 16 per subject

will be analysed descriptively on the safety analysis set by computing the number of treatment-emergent adverse events per subject by treatment group.

Trial ID: LP0145-2274 Date: **04-Jan-2023** Version: 5.0 Page 96 of 129

An event will be considered treatment-emergent if started after the first dose of IMP or if started before the first dose of IMP and worsened in severity after first dose of IMP. An event will not be considered treatment-emergent if starting 18 weeks after the last dose of IMP.

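### Section 11.4.4 withdraws a subject with a confirmed abnormal ECG from the trial, ending the planned collection of new AEs that stopping IMP alone would keep (minor)

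*Combined protocol and SAP*

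**What the plan says.** The combined protocol and SAP handles a confirmed, clinically significant ECG abnormality in two places.

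- Section 11.4.4 requires two actions: "If the ECG or change in ECG is confirmed clinically significantly abnormal, the subject must permanently discontinue IMP, and be withdrawn from the trial".
- Section 10.2.1, the list of reasons for stopping IMP permanently, has the entry "Confirmed clinically significantly abnormal ECG or change in ECG" and does not mention withdrawal.

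Section 10.1 treats these as different states. On withdrawal it says: "A subject who withdraws from the trial is a subject who stops treatment with the IMP and all further protocol defined trial activities". By contrast, someone who only stops IMP for good agrees to the follow-up in section 10.3.

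Section 10.3 then gives each state its own visits. After permanent discontinuation there is an early termination visit and also this: "An end of trial visit (safety follow-up visit 16 weeks after last administration of IMP". After withdrawal only the first is planned: "Subjects who withdraw from the trial after first dose of IMP for any reason will be asked to attend an early termination visit". Known AEs are followed under section 13.7 if the subject agrees.

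The secondary endpoint is the number of treatment-emergent AEs per subject from baseline to week 16. Section 14.3.6 analyses it "by computing the number of treatment-emergent adverse events per subject by treatment group".

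**The concern.** Section 12.2 explains that ECGs are collected because some large proteins may have indirect cardiac effects on long exposure. Under 11.4.4, a confirmed finding of that kind ends planned observation of the subject in whom it appeared. Panel 2 schedules an ECG, vital signs, physical examination, laboratory tests, ADA and PK at the final safety visit. A withdrawn subject has none of these after the termination visit, so the protocol would not show whether the abnormality resolved as the drug cleared.

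The endpoint is also exposed. A count per subject with no allowance for time observed is lower in a subject observed for less time, and here the shortening follows a safety event. With planned groups of 8 and 4, one such subject is a visible share of an arm.

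**Working it through.** **Inputs.** Panel 2 visit days: baseline 1, week 2 = 15, week 4 = 29, week 8 = 57, week 12 = 85, week 16 = 113. Scheduled on-treatment ECGs after baseline: weeks 4, 8, 12 and 16. Half-life 21 to 25 days (section 5.2, Pharmacokinetics). Safety visit after stopping IMP: 16 weeks after last dose (10.3).

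**The plan's own figure.** 16 × 7 = 112 days of planned safety observation after last dose for a subject who stops IMP early. Section 12.1 states the same 16 weeks.

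**Timing of the termination visit.** Section 10.3 asks for it as soon as possible after last administration. Section 7.1 places it "at the time of the decision to withdraw from the study", although that sentence stands under the safety follow-up period. Section 11.8 completes the end-of-trial form when the subject "has had their last visit (that is the safety follow-up visit 16, or early IMP termination visit", although 10.3 uses that name for the visit after stopping IMP. Neither sentence settles the date for a subject withdrawn during treatment. I therefore assume 0 to 14 days after the ECG visit, which leaves room for the repeat ECG and central reading.

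**Endpoint days lost.** The period is 113 − 1 = 112 days. Days lost = 113 − ECG day − delay.

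| ECG visit | Delay 0 days | Delay 14 days |
|---|---|---|
| Week 4 | 113 − 29 = 84 (75%) | 70 (62.5%) |
| Week 8 | 113 − 57 = 56 (50%) | 42 (37.5%) |
| Week 12 | 113 − 85 = 28 (25%) | 14 (12.5%) |

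A week 16 finding costs none of this period. For a whole arm, one week 4 case loses at most 84 / (8 × 112) = 9.4% of the planned LEO 138559 subject-days, or 84 / (4 × 112) = 18.8% of the comparator's. Over all 12 subjects it is 84 / 1,344 = 6.3%.

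**Observation after last dose.** With a delay of 0 to 14 days, withdrawal leaves 0 to 14 days if IMP was given at the ECG visit, or 14 to 28 days if that dose was withheld. The 10.3 route gives 112.

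**Drug remaining (LEO 138559 only).** Fraction = 2^(−t/h), relative to the level at the start of decay:

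- t = 14: 0.630 (h = 21) to 0.678 (h = 25)
- t = 28: 0.397 to 0.460
- t = 112: 0.025 to 0.045

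This is a simplification. Section 5.2 reports target-mediated disposition, with linear clearance dominant at and above 150 mg Q2W exposure, so the 112-day values are likely too high. Section 12.1 expects non-detectable levels in most subjects by then.

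**What the 10.3 route would recover.** For a week 4 finding the safety visit falls on day 15 + 112 = 127 (last dose week 2) or 29 + 112 = 141 (last dose week 4). Both are after day 113, so the whole endpoint period is covered, though by one visit with retrospective AE questioning.

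**The case against.** The strongest reply is that nothing here conflicts. Section 10.2.1 lists triggers for stopping IMP and does not promise that those subjects stay in the trial. Its entries include withdrawal by the subject, and pregnancy, for which 11.4.5.2 also requires withdrawal. Section 11.4.4 is the more specific rule and can be followed as written. This stands. A reader might infer that the two sections contradict each other and leave the site unable to comply, but the documents do not support that. The point is what compliance costs.

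Second, section 9.5 has the same structure: systemic rescue stops IMP and withdraws the subject. That is a sponsor choice and is not challenged here, nor is the rule on other biologics in 7.1. The ECG case differs because the trigger is itself a safety finding of the kind that 12.2 sets out to detect.

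Third, safeguards remain. The ECG event is recorded as an AE (11.4.4, Reporting in eCRF). Section 13.7 follows SAEs to a final outcome, and section 13.4.1 keeps later SAEs reportable within 24 hours if the investigator learns of them. Section 14.3.9.1 adds rates per 100 patient years, which allow for shorter observation. A reader might infer that all safety information is lost at once; it is not. But these provisions mostly concern events already known, or serious events that happen to reach the investigator. None restores planned collection of new AEs or the later ECG.

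Fourth, cases will be rare. Exclusion criterion 21 removes clinically significant ECG abnormalities at entry, and section 5.2 reports no nonclinical need for a QT study. This stands and limits the severity.

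**Conclusion.** The point holds, with minor severity. For an affected subject, 11.4.4 ends planned collection of new AEs at the early termination visit and removes up to 84, 56 or 28 of 112 endpoint days for a finding at week 4, 8 or 12. Those maxima assume the termination visit coincides with the ECG visit; a 14-day delay reduces them to 70, 42 and 14. The documents give no frequency for the trigger, so the expected loss for the trial cannot be computed and may well be zero.

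Two larger conclusions are not supported. A reader might infer that the primary endpoint is at risk. The first scheduled ECG after dosing is at week 4, the primary biopsy visit, so scheduled ECGs do not cut that endpoint short; only an unscheduled ECG before week 4 could. No formal test is affected, because none is planned.

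A reader might also infer that the 16 weeks in 10.3 should become 18. Completers are last seen 225 − 99 = 126 days (18 weeks) after the week 14 dose, against 112 days for early stoppers. But 10.3 and 12.1 both state 16 weeks after last dose, and 12.1 gives a reason. The 18 weeks in 14.3.6 limits which events count as treatment-emergent, and in inclusion criterion 11 it is a contraception period. Neither sets a visit.

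**What to change.** In section 11.4.4, replace the closing clause that withdraws the subject with: and be followed up as described for permanent discontinuation of IMP in Section 10.3. Subjects who choose to leave stay under the withdrawal paragraph of 10.3.

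The cost is one clause of text, and one already-defined safety visit kept for each affected subject. No analysis changes.

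Matching wording for pregnancy in 11.4.5.2 is optional. It would agree with 13.5.1, which speaks only of stopping IMP, but little is gained because pregnancies are already followed to outcome. Leave section 9.5, the biologics rule in 7.1 and the 16-week interval in 10.3 and 12.1 as they are.
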